4. Older adult for whom they provide support to has cognitive loss based on the results of the informant AD8 screening tool (AD8 score >2 to have cognitive loss);
5. Are involved in decision-making related to the healthcare and support of the older adult with cognitive loss; and
6. Have access and the ability to use a desktop or laptop computer with internet (the application is not currently mobile or tablet-friendly).

In **Aim 2**, participants will be eligible if they:

1. Are age 21 or older;
2. Speak and read English (NDR is currently not available in other languages);
3. Provide caregiving support (e.g. emotional, social, physical, task-related) to an older adult (>age 65) at least one hour per week;
4. Older adult for whom they provide support to has cognitive loss based on the results of the informant AD8 screening tool (AD8 score >2 to have cognitive loss);
5. Are involved in decision-making related to the healthcare and support of the older adult with cognitive loss;
6. Have access and the ability to use the internet to access the program (currently supported on mobile, tablet, laptop or desktop); and
7. Have a valid email address and/or willingness to create an email account for study purposes.

3.0 Sample Size:

Aim 1: We will recruit up to 15 family caregivers to participate in Aim 1. Data collected for Aim 1 will include both quantitative and qualitative data. Based on previous research it has been shown that 12-15 interviews are enough to reach thematic saturation in qualitative studies. Through our own experiences conducting qualitative studies, we anticipate reaching thematic saturation with this number.

Aim 2: We will recruit up to 150 family caregivers to participate. We will keep recruiting until we reach the target of 120 family caregivers who complete all the aim 2 activities, so we may recruit less than 150 participants. Proposed sample size is based off statistical power analysis which shows that n=120 will likely allow us to find

statistical significance if the studied effect(s) exist in the full population.

Recruitment and Screening Methods

Recruitment

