STATISTICAL ANALYSIS PLAN

Version Date: 3/12/2024

NCT04837937

Aim 2: Utilizing Multiphase Optimization Strategy (MOST), conduct a randomized pilot trial of the NDR intervention that targets better communication between caregivers and health teams, using a 23 full factorial design, to (2a) determine the feasibility of delivering the intervention, and (2b) derive estimates of the effect of 3 intervention components on changes in patient-centered outcomes at post-intervention and follow-up.

Exploratory Aim 3: Explore if intervention components (lectures/exercises) interact to change communication between caregivers and health care teams at post-intervention and follow-up.

Research Design: Randomized Pilot Trial (Aims 2 & 3). Aim 2 will use a 2³ full factorial trial design to test 3 binary components. Individuals will be randomized to 1 of 8 experimental conditions (Table 1). As shown in Table 1, participants can be assigned to intervention ("Yes") or control ("No") conditions for each component. Participants will be blinded to their experimental condition, but everyone will receive "caregiver-patient" negotiation exercise so that no participant gets an inactive placebo.

Unlike the two-arm RCT, the factorial trial compares combinations of conditions to test main effects of and interactions between exercises. For example, to test the main effect of the NDR exercise between caregiver-physician, conditions 1-4 are compared to conditions 5-8 (see **Data Analysis**). In this way, participants are "recycled" across conditions to contain the sample size.

Participants & Recruitment. We will plan to enroll 130 family caregivers in the study.

Procedure & Randomization. Interested individuals will complete a brief screen by telephone to assess potential eligibility. Potentially eligible individuals will be screened and invited to enroll in the intervention and consent using e-Consent. Randomization will be performed using study-ID embedded URL links a-priori to assign participants to an experimental condition with an 8:1 ratio.

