Table 1: Full Factorial Design

Experimental Condition	NDR Exercises by Relationship Conflict Content			
	Caregiver - Patient – Easy [Constant]	Caregiver-Caregiver	Caregiver-Physician	Caregiver - Patient – Difficult
1	Yes	No	No	No
2	Yes	No	No	Yes
3	Yes	No	Yes	No
4	Yes	No	Yes	Yes
5	Yes	Yes	No	No
6	Yes	Yes	No	Yes
7	Yes	Yes	Yes	No
8	Yes	Yes	Yes	Yes

Table 2: Study Components, Time-Points

Intervention		Follow-Up Surveys		
Baseline Survey (T1)	Intervention Completion	Post-NDR Survey (T2)	1 Month (T3)	3 Month (T4)

including themes of spirituality, meaning, mastery, and control, which provided the most important issues facing caregivers. The extensive care needs of individuals with AD are variable, and care typically involves great demands on spouses and other family members.¹¹⁹⁻¹²¹ By examining the wellbeing of the family caregiver as a primary outcome, we will be able to detect how the demands and care needs of their loved ones are affected by the interventions. In addition, among family caregivers of people with AD, there are high rates of anxiety, stress, and depression.^{122,123} Research has shown that poor caregiver mental health was associated with increased patient mortality, even after controlling for sex, age, dementia severity, and patient mental health.¹²⁴ Family caregivers experience anxiety when advocating for their loved ones health care needs.¹²⁵ NDR training may minimize anxiety. Thus, we will measure secondary outcomes of 1.) Anxiety (Patient-Reported Outcomes Measurement Information System (PROMIS) - Anxiety) and Neuro-QoL Caregiver-specific Anxiety¹²⁶ 2.) Caregiver Stress (Caregiver Stress Index), 3.) Caregiver Burden (Zarit Family Caregiver Burden Scale)¹²⁷ 4.) Fatigue (PROMIS)¹²⁸, 5.) Self-Efficacy as measured by PROMIS General Self-Efficacy and Caregiving Self-efficacy scales¹²⁹⁻¹³¹ and 6.) Received Support as measured by PROMIS Emotional/Informational Support, and Social Roles.

Table 3: Process and Patient-Centered Outcome Measures

Constructs	Measurement	Months		
		0	1	3
Patient Centered Outcomes				
Well-Being	(Primary outcome) Neuro-QOL – Positive Affect and Well-Being – Short Form	X	X	X
Anxiety	*PROMIS Ca Adult Item Bank Emotional distress-Anxiety; NEURO-QoL Caregiver Specific Anxiety	X	X	X
Satisfaction with Social Roles	PROMIS Ca Satisfaction with social roles/activities	X	X	X
Caregiver Burden	Zarit Family Caregiver Burden Scale	X	X	X
Fatigue	PROMIS Ca Fatigue	X	X	X

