Data Collection. We will utilize REDCap Surveys software for data entry.¹³² REDCap is a secure, encrypted, Web-based application designed to support data capture for research studies, providing 1) an intuitive interface for validated data

entry; 2) audit trails for tracking data manipulation and export procedures; and 3) automated export procedures for seamless data downloads to common statistical packages. This software allows for straightforward electronic entry of responses and can generate output data files compatible with statistical programs. Drs. [name] and [name] will oversee the database structure and quality assurance activities.

Data Analysis: Power Calculation. The goal of this research is to inform a RCT trial of an optimized intervention. We will achieve that goal by evaluating feasibility and generating effect sizes of each component on changes in outcomes. The effect sizes will inform which components to retain in the optimized intervention and be used to power a subsequent trial. The pilot trial is not powered for hypothesis testing; however, a power calculation was run to determine the effect size this pilot trial will be powered to detect. With 120 subjects total and 40 subjects in each component group, we will be able to detect effect sizes of 0.65 with 80% power using a two-sided t-test at a type I error rate of 5%. For the primary outcome of Neuro-QOL Positive Affect and Well-Being, this equates to a mean difference of 3.9, assuming a standard deviation of 6. Calculations employed Rochon's GEE method, as implemented in SAS GEESIZE v. 3.1 macro implemented by Dahmen.¹³³⁻¹³⁶

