Data Analyses: Aims 2 and 3 Quantitative. Data will be stored on a HIPAA-compliant server with secure access for approved study staff. Analyses will be conducted using SAS 9.4. For **Aim 2a**, we will calculate averages of acceptability ratings, number of exercises completed (retention to treatment), and prescribed strategies documented (compliance). These data will be used to derive expected usage rates for a future trial. For **Aim 2b**, we will assess the effect of each component on changes in Neuro-QOL – Positive Affect and Well-Being across time (baseline-1 month post-intervention), which will be done by comparing combinations of participants across conditions. Analyses will be conducted using intent-to-treat linear mixed effects models, accounting for data collected at multiple assessment time points nested within individual participants. For each component, we will test differences in change in outcomes across time, with baseline values as the reference. Thus, the effects will be modeled as component x time interactions. Cohen's *d* will be calculated by dividing the mixed effects model derived intervention effect estimate by the pooled standard deviation of the outcome. We will also report results disaggregated by sex and test sex as a moderator to evaluate sex differences in outcomes, which will inform the need for any sex-specific approaches in an optimized intervention. For **Aim 3**, exploratory analyses using linear mixed models will be performed to test two-way interactions between components on changes in weight and binge eating (e.g., Component 1 x Component 2 x time). Interaction tests are to determine if a set of components impact the overall effect and thus should be retained together in the optimized intervention.

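### The SAP's power statement uses 40 participants per component group, but every main effect in the 2×2×2 factorial compares about 60 with 60 of 120, so on the stated t-test basis the detectable effect is about 0.52 SD, not 0.65 SD

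*SAP*

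**What the plan says.** The SAP, under Data Analysis: Power Calculation, states: "With 120 subjects total and 40 subjects in each component group, we will be able to detect effect sizes of 0.65 with 80% power". The test is a two-sided t-test at the 5% level. With an SD of 6 for Neuro-QOL Positive Affect and Well-Being, the SAP gives the detectable difference as 3.9 points. The same paragraph attributes the calculation to a "GEE method, as implemented in SAS GEESIZE v. 3.1 macro", without a within-person correlation or any other input for that method.

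The design is set out elsewhere in the SAP. Research Design randomizes individuals to one of eight conditions formed by three binary components, and illustrates a main effect by saying that "conditions 1-4 are compared to conditions 5-8". The layout is in "Table 1: Full Factorial Design".

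On numbers, the SAP says "We will plan to enroll 130 family caregivers in the study". Protocol section 3.0 sets a ceiling of 150 recruits and says "We will keep recruiting until we reach the target of 120 family caregivers who complete all the aim 2 activities".

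For the analysis, the SAP (Data Analyses: Aims 2 and 3 Quantitative) uses intent-to-treat linear mixed models of change from baseline to 1 month, "with baseline values as the reference", and says "the effects will be modeled as component x time interactions".

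**The concern.** A full factorial is efficient because every participant contributes to every main effect. The SAP says so itself when it explains that participants are reused across conditions to keep the sample small. A group size of 40 is 120 divided by three, which would suit three separate component arms. That is not this design.

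This is the only power calculation shown in either document, and its purpose is to tell readers what size of component effect the pilot can detect. If the group size is wrong, the stated sensitivity does not describe the trial's contrasts. The trial's effect sizes are meant to decide which components are kept and to power the next trial, so readers need the sensitivity of the contrasts that will actually be estimated.

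**Working it through.** **Inputs.** From the SAP power paragraph: total 120, 40 per group, effect 0.65 SD, SD 6, 80% power, two-sided 5% t-test. From Table 1: eight conditions and three components. From Participants & Recruitment: 130 enrolled. Equal allocation is an assumption, because the 8:1 ratio given under Procedure & Randomization does not define an allocation over eight conditions.

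**Step 1: the plan's own figure.** The detectable effect for two equal groups of n is approximately (1.960 + 0.842) × √(2/n) in SD units. For n = 40 this is 2.802 × 0.2236 = 0.627. The exact noncentral-t value is 0.634 SD, or 0.634 × 6 = 3.8 points. Power at 0.65 SD with 40 versus 40 is 82%. The stated 0.65 is therefore close to a 40-versus-40 t-test that uses only 80 of the 120 participants. A 40-versus-80 split that uses all 120 gives 0.547 SD and does not reproduce it.

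**Step 2: group sizes in Table 1.**

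| Component | Yes | No |
|---|---|---|
| Caregiver-caregiver | 5, 6, 7, 8 | 1, 2, 3, 4 |
| Caregiver-physician | 3, 4, 7, 8 | 1, 2, 5, 6 |
| Caregiver-patient, difficult | 2, 4, 6, 8 | 1, 3, 5, 7 |

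Each component is four conditions against four. (The Research Design example attaches the 1-4 versus 5-8 contrast to caregiver-physician, whereas Table 1 gives it to caregiver-caregiver. The group size is the same.) With 120/8 = 15 per condition, 4 × 15 = 60 per side. Sets of one to four conditions hold 15, 30, 45 or 60 participants, never 40.

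**Step 3: detectable effect on the stated t-test basis (noncentral t).**

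| Comparison | Detectable effect | Points at SD 6 | Power at 0.65 SD |
|---|---|---|---|
| 40 vs 40 (as written) | 0.634 SD | 3.81 | 82% |
| 60 vs 60 (120 analysed) | 0.516 SD | 3.09 | 94% |
| 65 vs 65 (all 130 enrolled; 4 × 16.25) | 0.495 SD | 2.97 | 96% |

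A 64/56 split gives 0.517 SD, so modest imbalance does not matter. Fitting all eight cell parameters (112 degrees of freedom) leaves the 60-versus-60 figure at 0.516. An assumed 10% loss from 120 (54 vs 54) gives 0.544 SD.

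**Step 4: the planned component-by-time effect, 60 vs 60.** The SAP gives neither the within-person correlation ρ nor whether baseline means are constrained equal, so both are assumptions here. With free baseline means and raw change, multiply 0.516 by √(2(1 − ρ)). With baseline means constrained equal, multiply by √(1 − ρ²).

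| ρ | Free baselines | Constrained baselines |
|---|---|---|
| 0 | 0.73 SD | 0.52 SD |
| 0.2 | 0.65 SD | 0.51 SD |
| 0.5 | 0.52 SD | 0.45 SD |
| 0.7 | 0.40 SD | 0.37 SD |

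With free baselines, 0.65 SD is reached at ρ = 1 − (0.65/0.516)²/2 = 0.21. At 60 versus 60, a figure above 0.65 SD needs free baselines and a correlation below about 0.21.

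**The case against.** The strongest reply is that the t-test is only half of the stated basis. The SAP also names a GEE method, and with undisclosed inputs that method could have produced 0.65 legitimately: 60 versus 60 with free baselines and a correlation of 0.2 gives 0.65 SD. Nor is 0.52 SD the sensitivity of the planned analysis, which models change over time and could detect anything from 0.37 to 0.73 SD under the assumptions above. The 0.21 threshold is also specific to 60 versus 60; at 54 versus 54 it rises to 1 − (0.65/0.544)²/2 = 0.29. Finally, equal allocation and 120 analysed are assumptions. An intent-to-treat analysis may include more than the completers, and at the protocol's ceiling of 150 the comparison would be 75 versus 75, with 0.46 SD detectable.

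Most of this stands as a limit on what can be said about 0.65. The figure cannot be traced, and 0.52 SD should be labelled as the t-test value. It does not rescue the group size, because no choice of correlation makes a component group hold 40 in Table 1. The missing GEE inputs are a further reason to redo and document the calculation.

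It is also fair to say that little depends on the error. The SAP states that the pilot was not sized for formal testing, and no retention cut-off refers to 0.65.

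**Conclusion.** The point holds and is minor. The group size of 40 is wrong for this design. Under equal allocation each main effect compares about 60 with 60 of 120 participants. On the SAP's stated t-test basis the detectable effect is then about 0.52 SD (3.1 points at SD 6) rather than 0.65 SD (3.9 points), so the plan overstates it by about a quarter (0.65/0.516 = 1.26). The error is conservative on that basis, and the trial is not underpowered because of it.

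Confidence is high for the group size and for the t-test arithmetic. How 0.65 was obtained, and what the planned component-by-time model can detect, cannot be settled from the documents.

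**What to change.** In the SAP power paragraph, replace the statement of 40 per component group with text such as:

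> With 120 participants completing, out of about 130 enrolled and equally allocated to eight conditions, each component main effect compares about 60 with 60.

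Restate the detectable effect as about 0.52 SD (3.1 points at SD 6), labelled as the t-test value. Preferably, rerun the calculation for the planned component-by-time effect from baseline to 1 month, stating:

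- the within-person correlation;
- whether baseline means are constrained equal;
- whether N is the 120 completers or the 130 enrolled.

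Two related wording changes belong in the same edit. If equal allocation is meant, say so under Procedure & Randomization in place of the 8:1 ratio. Also align the sentence in protocol section 3.0 that presents 120 as likely to give statistical significance with the SAP's position that the pilot is not sized for hypothesis tests.

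The cost is one recalculation, a few wording changes in the SAP and one sentence in the protocol. No participants are added and the analysis model does not change.

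### The SAP's detectable effect (0.65 SD, 3.9 points) is credited to two methods, uses 40 per component group where the factorial gives 60 v 60, and is not tied to the planned test of change

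*SAP*

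**What the plan says.** The SAP section on the power calculation starts from "With 120 subjects total and 40 subjects in each component group" and concludes that the trial can "detect effect sizes of 0.65 with 80% power using a two-sided t-test at a type I error rate of 5" percent. For the primary outcome, Neuro-QOL Positive Affect and Well-Being, it adds that "this equates to a mean difference of 3.9, assuming a standard deviation of 6". The next sentence credits the calculation to Rochon's "GEE method, as implemented in SAS GEESIZE v. 3.1 macro". The same paragraph says that the pilot is not meant to support hypothesis tests, and that its effect sizes will guide which components are kept and the size of the next trial.

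The SAP's quantitative analysis section (Aims 2 and 3) plans a linear mixed model of change in well-being from baseline to 1 month: "Thus, the effects will be modeled as component x time interactions".

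The SAP's research design section and Table 1 set out eight conditions. Each of the three components is given in four and withheld in four, and a main effect compares one set of four with the other.

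Protocol section 3.0 cites a power analysis as support for n=120.

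**The concern.** A single number is attributed to two different calculations. A two-sample t-test needs a group size and an SD. A repeated-measures GEE calculation also needs a within-person correlation, the number of time points and the contrast of interest, and the SAP gives none of these. The planned test is a difference in change, so its precision depends on the correlation between baseline and 1 month. It also depends on whether the SD of 6 describes the score or the change, which is not stated.

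The group size does not fit the design either. Forty is 120 divided by three, as if the three components were three separate arms. In a full factorial every participant contributes to every component's comparison.

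This is the only precision figure in the SAP, and the protocol leans on a power analysis for its sample size. Anyone judging whether a component should be kept or dropped needs to know what difference the planned comparison can resolve.

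**Working it through.** **Inputs from the documents.** Two-sided alpha of 5%, 80% power, effect 0.65, SD 6, 120 participants and 40 per component group (SAP, power calculation). Four conditions against four (SAP, research design and Table 1). Change from baseline to 1 month (SAP, quantitative analysis). The protocol's target of 120 is a count of completers (section 3.0).

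**Assumptions.** The eight conditions are equal in size, so a component's main effect is 60 v 60. Data at 1 month are complete. The SD is the same at both times. The correlation rho between baseline and 1 month is not given, so 0.3, 0.5 and 0.7 are used.

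**Step 1: reproduce the SAP's figure.** Power comes from the noncentral t distribution with n1 + n2 − 2 degrees of freedom and noncentrality d / √(1/n1 + 1/n2).
- 40 v 40, d = 0.65: noncentrality 0.65 / √(1/40 + 1/40) = 2.91, power 81.9%.
- Smallest group size that reaches 80% power at 0.65: 39 (38 gives 79.9%).
- Effect detectable with exactly 80% power at 40 v 40: 0.634 SD, or 3.81 points.
- 0.65 × 6 = 3.9 exactly.

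The t-test figure is reproduced, with slightly conservative rounding. The GEE route cannot be run because its inputs are missing.

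**Step 2: use the design's own contrast.** Each component has 4 × 15 = 60 participants with it and 60 without.
- 60 v 60, d = 0.65: noncentrality 0.65 / √(1/60 + 1/60) = 3.56, power 94%.
- Detectable effect at 80% power, single time point: 0.516 SD, or 0.516 × 6 = 3.1 points.

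**Step 3: move to the planned test of change.** If 6 is the SD of the score, the SD of change is 6√(2(1 − rho)), and the detectable difference is 0.516 times that. If mean baseline well-being is constrained equal across randomised levels, or adjusted for, the effective SD is 6√(1 − rho²). The variance ratio of the second to the first is (1 − rho²) / (2(1 − rho)) = (1 + rho)/2.

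| rho (assumed) | SD of change | Detectable difference in change, 60 v 60 | Power for 3.9 points, 60 v 60 | Detectable with baseline constrained or adjusted | Variance ratio |
|---|---|---|---|---|---|
| 0.3 | 7.10 | 3.7 points (0.61 SD) | 85% | 2.95 points | 0.65 |
| 0.5 | 6.00 | 3.1 points (0.52 SD) | 94% | 2.68 points | 0.75 |
| 0.7 | 4.65 | 2.4 points (0.40 SD) | over 99% | 2.21 points | 0.85 |

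At 60 v 60, the unadjusted detectable difference rises to 3.9 points only when rho falls to about 0.21.

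If 6 is instead the SD of change, the detectable difference in change at 60 v 60 is 0.516 × 6 = 3.1 points whatever the correlation.

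**The case against.** The strongest defence is that nothing in the paragraph is miscalculated. That stands. A reader might infer from the exact value of 0.634 that 0.65 is an arithmetic error, but at 40 v 40 the trial does have at least 80% power at 0.65, and the gap is about 0.1 point on the safe side.

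A reader might also infer that 0.65 was computed for the wrong test. The documents do not show that. The GEE method named is a repeated-measures one, the same paragraph speaks of component effects on change, and an SD of 6 could be the SD of change. Against this, the SAP attaches the 6 to the primary outcome and plans to scale Cohen's d by the outcome's pooled SD, which points towards the score. The text leaves the question open, and that omission is the defect.

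Thirdly, the SAP disclaims power for hypothesis testing, so the number does not carry the weight it would in a confirmatory trial. This limits the consequence and is accepted. It does not remove it, because component decisions and the next trial's size are to rest on these estimates, and the protocol uses a power analysis to justify 120.

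Finally, the mixed model as planned is valid under randomisation. Constraining or adjusting for baseline is an efficiency gain and does not correct an error.

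**Conclusion.** The point holds as one of specification and of the design's stated precision. The SAP gives one detectable effect, names two methods for it, omits the correlation, the contrast and the meaning of the SD, and uses 40 per group where the factorial gives 60 v 60.

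The stated 3.9 points is larger than the design needs: 3.1 points at a single time point. For a difference in change with a score SD of 6, the detectable difference is 0.2 to 1.5 points below 3.9 over correlations of 0.3 to 0.7. These sizes rest on equal condition sizes, complete 1-month data, an SD of 6 at both times and the assumed correlations.

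It would be wrong to conclude that the trial is too small for 3.9 points. At 60 v 60, power for that difference in change is 85% or more across the assumed range. The stated figure needs correcting, and the recruitment target is unaffected.

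**What to change.** In the SAP's power paragraph:
- Name one method, the one that matches the planned mixed model.
- Replace the 40 per component group with 60 v 60 of 120.
- State the contrast (difference in change from baseline to 1 month), the assumed correlation range, and whether 6 is the SD of the score or of change.
- Restate the detectable effect. If 6 is the score SD, this is 3.7, 3.1 and 2.4 points at correlations of 0.3, 0.5 and 0.7.
- Use the same statement to support n=120 in protocol section 3.0.

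In the analysis section, constrain mean baseline well-being to be equal across randomised component levels, or adjust for it. The variance of the 1-month effect falls to (1 + rho)/2 of the change-score variance, 25% lower at a correlation of 0.5, and the detectable differences become 2.95, 2.68 and 2.21 points.

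The cost is SAP wording, one repeat of the power calculation and a small change to the model statement. Baseline well-being is already collected (protocol instrument table; SAP Table 3), so no new data are needed.

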After Cycle 1 and Cycle 2, which will only occur if needed, of usability testing are complete, we will email all study participants a link to the final NDR tool. If Cycle 3 is needed, participants will run through the NDR tool independently and then fill out an online survey hosted on REDCap. This survey will include a modified version of the USE Scale (a measure of usefulness, satisfaction, ease of use, and ease of learning) to measure the participant's final satisfaction with the tool. Additionally, we will ask participants to complete a brief, semi-structured interview over the phone to assess the overall NDR tool's acceptability, satisfaction, and overall impressions. This semi-structured interview will help enhance the quantitative data collected in Cycle 3.

Aim 2: All study timepoints will take place online (REDCap survey) with the exception of the study screener (phone) and e-CONSENT (participant will view online while research study coordinator is on the phone).

Baseline Survey 1: Participants who consent to participate in the study will be sent a link to the REDCap Baseline Survey 1 to their email address. The Research Study Coordinator will confirm that the Baseline Survey 1 link was received while they are still on the call with the participant after the e-Consent to ensure it was sent to the correct email address, was not in a Spam/Junk folder, etc. Participants will have 7 days to submit their completed Baseline Survey 1.

Anticipated participant time required to complete Survey 1: 35 minutes

Study Intervention - Assigned NDR Exercises: Once the completed Baseline Survey 1 is received from the study participant, the Research Study Coordinator will send them a unique study link which includes their embedded randomization assignment (pre-randomized) to their email. The link will give participants access to the study website, www.NegotiAge.com, as well as the negotiation platform where they will access their assigned NDR exercises, IAGO. Participants will have 14 days to complete their assigned exercises.

Anticipated participant time required to complete Study Intervention – Assigned NDR Exercises*: 10-30 minutes

*Participants will be randomized to which/how many negotiation activities they are required to do so we are providing a range of time.

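### Aim 2a averages the raw number of exercises completed, but the factorial assigns 1 to 4 exercises by condition, so the figure mixes assignment with adherence

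*SAP*

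**What the plan says.** The SAP section on quantitative analyses for Aims 2 and 3 plans, for Aim 2a, to average three things: acceptability ratings, the "number of exercises completed (retention to treatment"), and the strategies documented, as a measure of compliance. It continues: "These data will be used to derive expected usage rates for a future trial".

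The design section says "Aim 2 will use a 2³ full factorial trial design to test 3 binary components". Table 1 adds an easy caregiver-patient exercise that everyone receives. Protocol section 7.0 (Aim 2, Study Intervention) confirms that the number of exercises is part of the allocation: "Participants will be randomized to which/how many negotiation activities they are required to do".

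The SAP's list of intervention-centered outcomes and its Table 3 both name completion of the training exercises as a feasibility item, without saying what it is measured against. Neither document expresses completion as a share of the exercises assigned, plans it by condition or by exercise, or says over which participants the Aim 2a averages are taken.

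**The concern.** A count of completed exercises measures adherence only if everyone is asked to do the same number. Here the maximum is set by randomisation. One completed exercise is full adherence in condition 1 and 25% adherence in condition 8. On the planned measure, someone who does everything asked in condition 1 scores lower than someone who abandons half of the work in condition 8.

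Feasibility is the first part of Aim 2, and the SAP's power section names it with the effect sizes as the route to the next trial. Components will be kept or dropped, so the optimised package may well contain a number of exercises other than the pilot average. One overall mean count does not translate to that package and does not show which exercise participants leave out. Nor does it show whether completion falls as more is asked. That is a reasonable thing to want to know, since the payment in Protocol section 13.0 for the exercises plus Survey 2 is \$300 whatever the number assigned.

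**Working it through.** The documents state no expected or target completion figure, so there is nothing to reproduce.

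**Inputs.** Exercises assigned, from SAP Table 1: 1 in condition 1; 2 in conditions 2, 3 and 5; 3 in conditions 4, 6 and 7; 4 in condition 8. Equal allocation to the eight conditions is assumed. The per-exercise completion probability *p* is not given, so a range of 0.50 to 1.00 is used.

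**Ceiling set by the design.** With *k* the number assigned:

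- E[*k*] = (1 + 2 + 2 + 3 + 2 + 3 + 3 + 4)/8 = 20/8 = 2.5
- E[*k*²] = (1 + 3×4 + 3×9 + 16)/8 = 56/8 = 7
- Var(*k*) = 7 − 2.5² = 0.75, SD 0.87

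Full adherence therefore gives a mean of 2.5, with individual counts from 1 to 4.

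**What a mean of 2.0 conveys.** In this mix it is 2.0/2.5 = 80% of the exercises assigned. The same count would be 2.0/2 = 100% of a two-exercise package or 2.0/4 = 50% of a four-exercise package.

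**How much of the spread between people is assignment.** The assignment part is *p*²×0.75. The behaviour part is 2.5*p*(1−*p*) if exercises are completed independently, or 7*p*(1−*p*) if a person does all or none.

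| *p* | Assignment share, independent | Assignment share, all-or-none |
|---|---|---|
| 0.95 | 85% | 67% |
| 0.90 | 73% | 49% |
| 0.80 | 55% | 30% |
| 0.70 | 41% | 20% |
| 0.50 | 23% | 10% |

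Assignment exceeds half only when *p* is above 2.5/3.25 = 0.77 (independent) or 7/7.75 = 0.90 (all-or-none).

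**If only completers were averaged.** Protocol section 3.0 recruits to 120 people who complete all Aim 2 activities. Among such people each count equals the number assigned, so the mean describes only the mix of conditions. It is 2.5 if completion is unrelated to the number assigned.

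**What one overall figure hides.** Two illustrative patterns of completion for 1/2/3/4 exercises assigned:

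- 95/90/80/60%: mean (0.95 + 6×0.90 + 9×0.80 + 4×0.60)/8 = 15.95/8 = 1.99; pooled 1.99375/2.5 = 79.8%
- 60/70/80/95%: mean (0.60 + 6×0.70 + 9×0.80 + 4×0.95)/8 = 15.80/8 = 1.98; pooled 1.975/2.5 = 79.0%

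The overall figures almost coincide, yet the four-exercise condition is at 60% in one and 95% in the other. The choice of rate also matters. Averaging each person's own rate gives 6.65/8 = 83.1% and 6.05/8 = 75.6%, against pooled rates of 79.8% and 79.0%.

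**Precision.** With the SAP's 130 enrolled, each condition has 130/8 ≈ 16 people. At 80% completion the approximate 95% half-width is 1.96×√(0.8×0.2/16) = 0.196, about 20 points. Each experimental exercise is assigned in four of the eight conditions, about 65 people: 1.96×√(0.16/65) = 0.097, about 10 points.

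**The case against.** The best defence is that this is a missing definition in a descriptive pilot analysis. The SAP speaks of deriving usage rates from these data, which leaves room for a division step. It lists exercise completion separately as a feasibility outcome. Protocol section 7.0 frames the work as completing the assigned exercises, and staff see completion status in an automated report. No progression threshold or component decision uses the average, and nothing is lost or biased by the present wording.

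Much of this stands. The information will exist, and the stakes are moderate. But room for a rate is not a specified rate. The statistic actually named is an average count, and followed as written it ranks participants wrongly on adherence.

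Two stronger readings should be resisted. A reader might infer that the average mostly reflects assignment. The documents give no completion rate, and assignment accounts for more than half of the between-person variance only at high completion (above about 77% or 90%, by model) or if only completers are averaged. Moreover, with a fixed allocation the mean number assigned is a known constant, so a fall in the overall mean below 2.5 does reflect non-completion, apart from chance imbalance between cells.

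A reader might also infer that the planned figure cannot give a usage rate. With equal cells, dividing the mean by 2.5 gives the pooled rate.

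It is also fair to say that a breakdown by number assigned will be imprecise, because the one-exercise and four-exercise groups are single conditions of about 16 people.

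**Conclusion.** The point holds as a deficiency in how the Aim 2a measure is defined, and it should be corrected. As written, retention to treatment is a count whose maximum varies from 1 to 4 by randomisation, with no denominator. Under equal allocation its ceiling is 2.5, and a mean of 2.0 corresponds to 80% pooled completion in this particular mix. It cannot be applied unchanged to a package of another size and does not identify the exercise that is dropped.

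The figures of 2.5 and 80% depend on equal cells. The SAP's 8:1 wording does not settle this, and unequal allocation would change both. The completion patterns in the check are illustrations, not forecasts. The primary outcome analysis is unaffected.

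**What to change.** In the Aim 2a paragraph of the SAP, replace the average number of exercises completed with:

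1. Exercises completed divided by exercises assigned, among all randomised participants, stating whether this is the mean of individual rates or the ratio of totals; and the percentage who complete everything assigned.
2. The completion percentage for each exercise among those assigned to it.

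State that the future trial's usage rates come from these two items. A table by number assigned (1, 2, 3, 4) can be added as description only, with its intervals shown, given about 16 people in each of the two extreme conditions. State the allocation ratio across the eight conditions plainly.

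The cost appears to be SAP wording only. Assignment is embedded in each participant's study link, and the automated report already shows who has completed all assigned exercises. That completion is recorded exercise by exercise is an inference from the SAP's plan to count exercises, and should be confirmed with those who run the platform.
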